### 10.1.3. Handling of Missing Data

Adverse events with missing start or end dates (for AEs that are not recovering/resolving) will be imputed according to the method described in Section 8.3. The original dates will be shown in listings.

## 10.1.4. Summary Tables

The following AE summary tables will be provided for each sub-trial (D/ND), where the numbers and percentages of participants, and numbers of events are included.

- TEAEs by SOC and PT
- TEAEs leading to study intervention discontinuation by SOC and PT
- TESAEs by SOC and PT
- TESAEs by SOC and PT (number of participants and occurrences)
- · TE AESIs by category, subcategory, and PT

| Hemoglobin               | MMOL/L (FE)           | G/L     | 16.1134           |
|                          | MMOL/L                | G/L     | 16.1134           |
|                          | G%                    | G/L     | 10                |
|                          | 1000/UL               | GI/L    | 1                 |
|                          | 10^3/UL               | GI/L    | 1                 |
|                          | /MM3                  | GI/L    | 0.001             |
|                          | K/CUMM                | GI/L    | 1                 |
|                          | THOU/CUMM             | GI/L    | 1                 |
|                          | 10^9/L                | GI/L    | 1                 |
|                          | GI/L                  | GI/L    | 1                 |
|                          | CELLS/MM  | GI/L    | 0.001             |
| Platelet Count           | THOU/MCL              | GI/L    | 1                 |
| WBC - Total              | PER CUMM              | GI/L    | 0.001             |
| Lymphocytes              | 10^5/CUMM             | GI/L    | 100               |
| Monocytes
Eosinophils | K/UL                  | GI/L    | 1                 |
| Basophils                | /MCL                  | GI/L    | 0.001             |
| Neutrophils              | /NL                   | GI/L    | 1                 |
| Erythrocytes - RBCs      | 10^3/CUMM             | GI/L    | 1                 |
|                          | KCELLS/UL             | GI/L    | 1                 |
|                          | 10^3/MM3              | GI/L    | 1                 |
|                          | CELLS/UL              | GI/L    | 0.001             |
|                          | 10^4/UL               | GI/L    | 10                |
|                          | 10^6/L                | GI/L    | 0.001             |
|                          | B/L                   | GI/L    | 1                 |
|                          | CELLS/NL              | GI/L    | 1                 |
|                          | THOU/UL               | GI/L    | 1                 |
| MCV                      | FL                    | FL      | 1                 |
| MCH                      | PG                    | PG      | 1                 |
| Deticularita             | 10^12/L               | TI/L    | 1                 |
| Reticulocytes            | 10^6/UL               | TI/L    | 1                 |
|                          | 10^4/UL               | TI/L    | 0.01              |

This document is confidential.

SAP Version: SAP V1.0 23-Jan-2025 Controlled Document ID: CG E Filing requirements: TMF Effective Date 31-Aug-2020

Sponsor: GlaxoSmithKline Research & Development Limited; Protocol No.: 214066/Protocol Amendment 02

| Laboratory Parameters   | Units     | SI Unit | Conversion Factor |
|---|-----------|---------|-------------------|
|   | CELLS/MM3 | TI/L    | 0.0000001         |
|   | 10^6/CUMM | TI/L    | 1                 |
|   | MIL/MM3   | TI/L    | 1                 |
|   | MILL/MCL  | TI/L    | 1                 |
|   | CELLS/UL  | TI/L    | 0.0000001         |
|   | CELLS/PL  | TI/L    | 1                 |
|   | MILL/UL   | TI/L    | 1                 |
|   | CELLS/NL  | TI/L    | 0.001             |
|   | 10^3/UL   | TI/L    | 0.001             |
|   | K/UL      | TI/L    | 0.001             |
|   | CELLS/MCL | TI/L    | 0.0000001         |
|   | TI/L      | TI/L    | 1                 |
|   | 10^3/CUMM | TI/L    | 0.001             |
|   | GI/L      | TI/L    | 0.001             |
|   | THOU/CUMM | TI/L    | 0.001             |
|   | 10^9/L    | TI/L    | 0.001             |
|   | THOU/UL   | TI/L    | 0.001             |
|   | 10^6/MM3  | TI/L    | 1                 |
|   | /MM3      | TI/L    | 0.0000001         |
| Lymphocytes % Monocytes % Eosinophils % Basophils % Neutrophils % | %         | %       | 1                 |
|   | Ratio     | %       | 100               |

Abbreviations: SI = International System of Units; WBC = White Blood Cell; RBC = Red Blood Cell; MCV = Mean Corpuscular Volume; MCH = Mean Corpuscular Hemoglobin

In the event that a site will only be able to provide WBC count with differential (Neutrophils, Lymphocytes, Monocytes, Eosinophils and Basophils) results in either % or absolute value, the formulas below will be used to convert between results in % and absolute value. Actual values and changes from baseline in both % and absolute value will be summarized by visit. However, the summary of numbers and percentages of participants with normal or abnormal WBC count with differential results and the listing of subjects with any abnormal hematology results will be only based on the original parameter, results of which are reported by sites.

Neutrophils/Lymphocytes/Monocytes/Eosinophils/Basophils % = (Absolute Value of Neutrophils/Lymphocytes/Monocytes/Eosinophils/Basophils / Absolute Value of WBC Total) × 100

Absolute Value of Neutrophils/Lymphocytes/Monocytes/Eosinophils/Basophils = Neutrophils/Lymphocytes/Monocytes/Eosinophils/Basophils % × Absolute Value of WBC Total / 100

This document is confidential

SAP Version: SAP V1.0 23-Jan-2025

Effective Date 31-Aug-2020 Controlled Document ID: CC

Sponsor: GlaxoSmithKline Research & Development Limited; Protocol No.: 214066/Protocol Amendment 02

Participants with any abnormal hematology and clinical chemistry results will be displayed in a listing.

|                            | MG/L      | UMOL/L  | 1.71              |
|                            | IU/L      | IU/L    | 1                 |
|                            | MMOL/H/L  | IU/L    | 16.663            |
| ALT                        | MCKAT/L   | IU/L    | 58.824            |
| ALI                        | MCMOL/SL  | IU/L    | 58.824            |
|                            | MCMOL/HML | IU/L    | 16.663            |
|                            | UKAT/L    | IU/L    | 58.824            |
|                            | IU/L      | IU/L    | 1                 |
| ALP                        | UKAT/L    | IU/L    | 59.988            |
|                            | MCKAT/L   | IU/L    | 59.988            |
| AST                        | IU/L      | IU/L    | 1                 |

<sup>3 Hepatocellular injury is defined as [ALT/ALT ULN) / (ALP/ALP ULN)] > 5 and ALT >3×ULN where ALT and ALP values must occur on the same day.

This document is confidential.

SAP Version: SAP V1.0 23-Jan-2025

Controlled Document ID: CC Effective Date 31-Aug-2020

Filing requirements: TMF

Page 38 of 59

Sponsor: GlaxoSmithKline Research & Development Limited; Protocol No.: 214066/Protocol Amendment 02

| Laboratory Parameters | Units         | SI Unit | Conversion Factor |
|-----------------------|---------------|---------|-------------------|
|                       | MCKAT/L       | IU/L    | 59.988            |
|                       | UKAT/L        | IU/L    | 59.988            |
|                       | G/L           | G/L     | 1                 |
|                       | G/DL          | G/L     | 10                |
| Total Protein         | MG%           | G/L     | 0.01              |
|                       | G%            | G/L     | 10                |
|                       | MG/DL         | G/L     | 0.01              |
|                       | Fraction of 1 | 1       | 1                 |
| INR                   | %             | 1       | 0.01              |
|                       | Ratio         | 1       | 1                 |

Abbreviations: SI = International System of Units; ALT = Alanine Aminotransferase; ALP = Alkaline Phosphatase; AST = Aspartate Aminotransferase; INR = International Normalized Ratio

Table 5 – PCIs for Laboratory Parameters of Liver Chemistry

| Laboratory Parameters | PCI   |        |  |
|-----------------------|-------|--------|--|
| Laboratory Parameters | Lower | Upper  |  |
| ALT                   | NA    | ≥3×ULN |  |
| Bilirubin             | NA    | ≥2×ULN |  |
| INR                   | NA    | >1.5   |  |

PCIs for the parameters not included in Table 5 are identical to the lower and upper normal ranges provided by local sites.

#### 10.4. Vital Signs

Vital signs will include systolic and diastolic BP and HR, which will be taken during all scheduled visits according to the Schedule of Activities in Table 1. BP and HR will be assessed using an appropriate size cuff, the assessment of which should be preceded by at least 5 minutes of rest for the participant in a quiet setting without distractions (e.g., television, cell phones). Three consecutive BP measurements will be obtained, of which the median will be recorded and be used for summary purposes. Descriptive statistics will be provided for the actual values of systolic BP, diastolic BP and HR at each study visit as well as change from baseline for each sub-trial (D/ND). All vital signs will be displayed in a listing for each sub-trial (D/ND).

#### 10.5. **ECG**

A 12-lead ECG will be administered only during screening visit with participants in supine position. HR, PR interval, QRS duration and QR (uncorrected) interval will be measured. QTcF will be calculated (machine read or manually). If prolonged QT/QTcF is noted, two additional ECG measurements should be obtained, the mean results of which will be used for determining whether eligibility criteria are met for inclusion. There is no QT stopping criteria and no further ECG monitoring is required during subsequent study visits unless indicated as part of routine care of the participants. ECG results will not be displayed in any outputs.

This document is confidential

SAP Version: SAP V1.0 23-Jan-2025

Controlled Document ID: CC Effective Date 31-Aug-2020

Page 40 of 59

Statistical Analysis Plan for Interventional Studies

Sponsor: GlaxoSmithKline Research & Development Limited; Protocol No.: 214066/Protocol Amendment 02

## 10.6. Physical Examination

Height (in cm) and weight (in kg) will be measured at each study visit according to the Schedule of Activities specified in Table 1. Descriptive statistics will be provided for the actual values of height and weight at each study visit as well as change from baseline by age group. Any unexpected persistent change in trajectory of height/weight should be recorded as an AE. All height and weight assessments will be displayed in a listing.

A complete physical examination will be performed during study visits specified in Table 1, including, at a minimum, assessments of the ears, nose and throat, skin, cardiovascular, respiratory, GI and neurological systems. Physical examination findings will not be displayed in any outputs.

This document is confidential.

SAP Version: SAP V1.0 23-Jan-2025

Controlled Document ID: CCI Effective Date 31-Aug-2020

Page 41 of 59

Statistical Analysis Plan for Interventional Studies

Sponsor: GlaxoSmithKline Research & Development Limited; Protocol No.: 214066/Protocol Amendment 02

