## 8.2.1. Physical Examinations

Children and adolescents with CKD, particularly those with ESKD, are frequently growth impaired, so at a given age, they can often be expected to have the weight of a smaller/younger child/adolescent.

Height (or supine length in the very young) and weight will be measured at each study visit as appropriate for the participant's age and plotted on age and gender appropriate charts as per SoC at that site, for example using height z scores for chronological age and body mass index (BMI) z scores for height age (the age corresponding to the 50th percentile of the participant's measured height) as a means of monitoring percentile-parallel growth and weight gain. Any unexpected persistent change in trajectory, should be recorded as an AE.

The investigator should contact the medical monitor if any participant's weight falls below that specified as the minimum weight for their age group (see Table 12).

A complete physical examination will include, at a minimum, assessments of the ears, nose and throat, skin, cardiovascular, respiratory, GI and neurological systems.

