#### 9.3.2.2. Secondary Safety Analyses

All secondary safety endpoints will be summarized descriptively separately in each subtrial (ND/D) overall and where appropriate within each age group.

Change from baseline in vital signs (BP and HR), height, weight and laboratory safety data (urea/BUN, creatinine, electrolytes, liver function tests [LFTs], calcium and full blood count with differential) will be summarized descriptively.

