# 5.2. Secondary Safety Endpoints

Changes from baseline in laboratory safety parameters, blood pressure (BP), heart rate (HR), height and weight at each time point for each sub-trial (D/ND).

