## 14. Changes from Analysis Planned in Protocol

Due to study being terminated early, all results will be displayed for each sub-trial (D/ND) unless otherwise specified and will not be split by age group, since all participants enrolled are from the 12 to <18 years group.

The originally planned analyses for the tertiary endpoints below will not be implemented due to limited data availability.

- During the study, the incidence of other health outcomes of interest related to
  - o Change in kidney function/intervention:
    - Transplantation
    - ESKD for ND participants
    - Switch between dialysis modalities for D participants
  - Other:
    - Death
    - Thrombosis
    - All-cause loss of vascular access patency
  - Participant related Palatability and Acceptability Questionnaire:
    - Palatability rating (good, acceptable, neither good nor bad, bad, very bad).
    - Ease of swallowing (very easy, easy, neither easy nor difficult, difficult, very difficult).

This document is confidential.

SAP Version: SAP V1.0 23-Jan-2025

Controlled Document ID: CC Effective Date 31-Aug-2020 Filing requirements: TMF

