#### 18.3. Safety

| Number | Table Name  | Analysis
Population |
|--------|---|------------------------|
| 3.1    | Summary of Treatment-Emergent Adverse Events by System
Organ Class and Preferred Term  | (Safety Set)           |
| 3.2    | Summary of Treatment-Emergent Adverse Events Leading to Study
Intervention Discontinuation by System Organ Class and Preferred
Term | (Safety Set)           |
| 3.3    | Summary of Treatment-Emergent Serious Adverse Events by
System Organ Class and Preferred Term  | (Safety Set)           |
| 3.4    | Summary of Treatment-Emergent Serious Adverse Events by
System Organ Class and Preferred Term (Number of Subjects and
Occurrences)  | (Safety Set)           |
| 3.5    | Summary of Treatment-Emergent Adverse Events of Special Interest by Category, Subcategory and Preferred Term                              | (Safety Set)           |
| 3.6    | Summary of Hematology Results by Visit and Changes from Baseline  | (Safety Set)           |
| 3.7    | Summary of Hematology Results Relative to Normal Range, Post-
Baseline Relative to Baseline by Visit                                   | (Safety Set)           |
| 3.8    | Summary of Clinical Chemistry Results by Visit and Changes from Baseline  | (Safety Set)           |
| 3.9    | Summary of Clinical Chemistry Results Relative to Normal Range,
Post-Baseline Relative to Baseline by Visit                            | (Safety Set)           |
| 3.10   | Summary of LFTs (+INR) Results by Visit and Changes from Baseline   | (Safety Set)           |

This document is confidential.

SAP Version: SAP V1.0 23-Jan-2025 Controlled Document ID: CG EFiling requirements: TMF

Effective Date 31-Aug-2020

| Number | Table Name   | Analysis
Population |
|--------|--|------------------------|
| 3.11   | Summary of Vital Signs by Visit and Change from Baseline | (Safety Set)           |

This document is confidential.

SAP Version: SAP V1.0 23-Jan-2025 Controlled Document ID: Effective Date 31-Aug-2020 Filing requirements: TMF

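### By-visit height and weight outputs promised in SAP 10.6 are missing from the table and listing indexes, and the planned summary is raw cm and kg change, which in growing adolescents cannot be read without an age- and sex-standardized value

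*SAP*

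**What the plan says.** The protocol's secondary safety analysis (9.3.2.2) covers "Change from baseline in vital signs (BP and HR), height, weight and laboratory safety data", summarized descriptively. SAP 5.2 keeps height and weight change at each time point as a secondary safety endpoint for each sub-trial (dialysis, D, and non-dialysis, ND).

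SAP 10.6 fixes the scale: "Height (in cm) and weight (in kg) will be measured at each study visit". It then commits to outputs: "Descriptive statistics will be provided for the actual values of height and weight at each study visit". The sentence goes on to promise differences from the starting value too, and here it brings in the age split: "as well as change from baseline by age group". A separate sentence commits to a listing of all height and weight assessments, with no age-group qualifier. SAP 8.2 defines change as a simple difference, and the SAP specifies no z-score, percentile or growth velocity.

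The nearest entry in SAP 18.3 is Table 3.11, "Summary of Vital Signs by Visit and Change from Baseline"; the nearest in SAP 20 is Listing 16.21, also vital signs. SAP 14 says that results "will not be split by age group", because everyone enrolled is aged 12 to under 18 years; SAP 5 and 8.1 say much the same.

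Protocol 8.2.1 notes that children with CKD are often growth impaired. It has sites plot growth on age- and sex-appropriate charts under local standard of care, "for example using height z scores for chronological age" and BMI z-scores for height age. Both documents ask for a sustained, unexpected departure from trajectory to be recorded as an adverse event.

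**The concern.** There are two linked problems. First, the text of the SAP and its indexes disagree about whether a declared paediatric safety endpoint will be reported. Programmers usually work from the index, so an output promised only in the text can be lost without anyone having decided to drop it.

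Second, if the table is produced as described, its scale is hard to interpret. Expected growth over 52 weeks differs widely between ages 12 and 17 and with sex and puberty. A mean raw change over a few participants mostly reflects who was enrolled, and a child who is falling behind can still show a gain. The information needed to tell these cases apart is collected but not used.

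**Working it through.** The plan states no figure for this endpoint, so the check is mainly a comparison of sections.

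**1. Does an indexed output exist?**

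| Place in SAP | Content | By-visit height/weight? |
|---|---|---|
| 10.6 | Statistics by visit, change from baseline, listing | Promised |
| 18.3, Tables 3.1 to 3.11 | Adverse events, laboratory, liver, vital signs | 0 of 11 |
| 19.2, Figures 3.1 and 3.2 | ALT and bilirubin plots | None |
| 20, Listings 16.1 to 16.24 | Includes 16.21, vital signs | 0 of 24 |
| 9.3 (Table 1.3, Listing 16.6) | Height, weight and BMI with demographics | Screening height and weight only |

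Table 3.11 and Listing 16.21 do not fill the gap as written. SAP 10.4 defines vital signs as blood pressure and heart rate, and the opening of SAP 10 names height and weight as an item separate from vital signs.

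**2. Was the output dropped on purpose?** Where the SAP drops an output, it says so: medical history (9.5), ECG (10.5), physical examination findings (10.6), kidney outcomes (13.2), thrombosis and access patency (13.3) and the questionnaire (13.4). Section 10.6 itself withholds examination findings while promising height and weight. Section 14 is silent on them. An omission from the index is the more natural reading.

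**3. Age-group wording.** SAP 5, 8.1 and 14 display results by sub-trial. With one age group enrolled, a split by age gives a single group, so nothing is distorted. But the sentence in 10.6 does not mention the sub-trial, which SAP 5.2 requires.

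**4. What does a raw change say?** Write observed gain = expected gain − deficit. The documents give no expected gain, so assume 0 to 8 cm in 52 weeks. An observed gain of 2 cm then means:
- if 2 cm was expected, a deficit of 2 − 2 = 0 cm;
- if 8 cm was expected, a deficit of 8 − 2 = 6 cm.

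The same raw value fits normal growth and marked faltering. A z-score for age and sex separates the two: its change is zero when a child keeps to the same centile and negative when the child falls behind.

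**5. Can z-scores be derived?** Yes. Month and year of birth are available (SAP 8.4), sex is collected (SAP 9.3), and height and weight are measured at every visit.

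**6. What could a group summary show after the change?** The pharmacokinetic analysis plan bound with the SAP (its Section 1.1) states that 4 adolescents were enrolled. The design is single arm (SAP 4.4). The 95% half-width for a mean change, in SD units, is t(0.975, n−1)/√n:
- n = 4, all pooled: 3.182/2 = 1.59 SD;
- n = 3: 4.303/1.732 = 2.48 SD;
- n = 2: 12.706/1.4142 = 8.98 SD.

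The D/ND split is not given, so 3 and 2 are assumed sub-trial sizes; a sub-trial of 1 would give no interval. The multipliers apply on either scale.

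**The case against.** The strongest reply is that the SAP implements what the protocol asks for. The protocol endpoint is change from baseline, summarized descriptively, and z-scores appear only as an example of site charting. Raw change is therefore not a departure from the protocol, and z-scores are an improvement rather than the correction of an error. That stands.

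A reader might go further and infer that height and weight have no planned output at all, so that the endpoint cannot show a growth effect. The documents do not support this, for four reasons:
- SAP 10.6 promises both the statistics and a listing. The defect is a mismatch between text and index.
- The shells are in a separate document (SAP 21) and could carry these variables, although the SAP does not say so.
- A raw listing, read with age and sex, would show each trajectory. A persistent departure is also to be reported as an adverse event and, if treatment-emergent, would appear in Table 3.1 and Listing 16.9.
- A group effect is out of reach mainly because there are 4 participants and no control, not because of the scale. Z-scores can also fall through CKD itself, so without a comparator they do not isolate a drug effect.

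It is also fair that the age-group phrase does no harm with a single age group. What survives is the unreconciled index and a summary that is hard to read without standardization.

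**Conclusion.** The point holds as an inconsistency within the SAP plus a weak choice of scale. A declared secondary safety endpoint is promised by-visit statistics and a listing in the text, but has neither in the indexes (0 of 11 safety tables, 0 of 24 listings), and no statement drops it. As planned, the summary mixes normal growth with any deficit across ages 12 to under 18 years.

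It should be corrected, but its reach is modest. Standardized values would make four individual trajectories interpretable. They would not support inference about a group effect: the half-width is 1.59 SD at best.

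The conclusion rests on the SAP as written, without sight of the shells. The growth range of 0 to 8 cm and the sub-trial sizes of 2 and 3 are assumptions used only for illustration.

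**What to change.** - Add to SAP 18.3 a table of height and weight by visit and change from baseline, by sub-trial.
- Add to SAP 20 a per-participant listing of all height and weight assessments, by sub-trial.
- In both, show raw values beside height and weight z-scores for age and sex, from one growth reference named in SAP 10.6.
- If BMI z-scores are added, state whether they are for chronological age or height age, since the protocol's example uses height age.
- In SAP 10.6, replace the age-group wording with by sub-trial.
- If the sponsor instead means to drop these outputs, SAP 14 should say so and give the reason.

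The cost is the z-score derivation from data already collected, one table and one listing. The small downside is having to choose and justify a growth reference.
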